# 2.3. Benefit/Risk Assessment

The purpose of the PRO-MERIT trial is to test prostate cancer-associated antigens encoded in BNT112 for the first time in patients with different stages of prostate cancer.

As of today, the RNA-LPX based cancer vaccines have been administered in more than 270 patients with melanoma, triple negative breast cancer (TNBC), and human papilloma virus (HPV)+ cancers and demonstrated a favorable safety and tolerability profile in different indications, different treatment settings (metastatic, post neo-adjuvant, adjuvant) and with different types of cancer vaccine antigens. In these clinical trials, no dose-limiting toxicities (DLTs) were reported during dose escalation, the TEAEs considered related to trial drug were transient, mostly Grade 1 and 2, and likely associated with the specific format of encoding and delivering the vaccine antigens, namely single-stranded RNA formulated as a DOTMA (1,2-di-O-octadecenyl-3-trimethylammonium propane)/DOPE (1,2-Dioleoyl-sn-glycero-3-phosphoethanolamine) lipoplex. In summary, the class-intrinsic safety profile of RNA-LPX *per se* appears to be dominated by mild-to-moderate, transient and manageable influenza-like AEs. These AEs are expected based on the distinct range of cytokines released by RNA-LPX. In addition, transient lymphopenia (by sequestration) observed in laboratory examinations is expected to be mediated by Type 1 IFN.

In addition to RNA-LPX class-intrinsic risks, potential risks related to the individual vaccine antigen targets are to be considered, which may potentially result in "on-target/off-tumor" toxicities mediated by the respective antigen-specific T cells. As the targets for the proposed prostate cancer trial were not used before in conjunction with the RNA-LPX format, the risk of on-target/off-tumor toxicity cannot be deduced from the ongoing trials. This risk is mitigated by selecting antigens with exquisitely cancer cell selective expression and lack of expression in vital normal tissues. The same pipeline has been used to select the cancer type specific vaccine antigens in the other ongoing RNA-LPX trials. Moreover, 2 of the 5 selected vaccine antigens have been used in trials by other sponsors in conjunction with other vaccine formats without indications of autoimmunity. Therefore, the risk of on-target/off-tumor toxicity is considered low.

Given that the Good Laboratory Practice (GLP) toxicology studies did not identify a no observed adverse effect level, the maximum dose (i.e., pg total RNA) used safely in humans in the melanoma trials justifies the entire proposed dose range for the proposed trial.

The planned trial will address in the safety program potential risks of both the vaccine format (considered low based on aggregate data from all RNA-LPX trials conducted by the sponsor), and immunopathology associated with T cells induced against the individual vaccine targets (considered low based on the sponsor's ongoing clinical trials and cumulative data in the public domain from other vaccine trials).

CONFIDENTIAL Page 41 of 122

Part 1 (dose titration) of the PRO-MERIT trial has been performed in the UK and Hungary and enrollment has been completed with 9 patients dosed. The SRC reviewed the available safety data for patients in Part 1 on 17 MAY 2021. The safety profile observed indicates that BNT112 is a tolerable drug product with a manageable safety profile at the defined dose range ( to µg) using the intra-patient step-up dose titration scheme. Observed AEs considered related to the IMP (including pyrexia, flu-like symptoms, hypertension, nausea, chills or headache), are in line with the innate immune activation by RNA-LPX, are transient in nature and manageable by analgesics, antipyretics or fluids at recommended and usual doses. The recommendation was to continue to Part 2 at the selected REDR ( US) using the intra-patient step-up dose titration scheme.

The annual review of safety data for the IB update occurred on 20 MAY 2021 (data extraction date) and included safety data from patients in Part 1 as well as Part 2. Neither the safety profile nor the benefit-risk assessment were changed.

The sponsor's ongoing Lipo-MERIT Phase 1 clinical trial in melanoma (NCT02410733) has provided promising signals for single agent and anti-PD-1 combination activity of RNA-LPX cancer vaccine against melanoma-shared antigens in pretreated checkpoint inhibitor-experienced patients with high medical need and limited treatment options. It has further demonstrated that in almost every patient the vaccine executes its MoA, inducing T cells against at least one of the antigens. A considerable fraction of these immune responses was strong (measurable *ex vivo*) and both new T cells were primed and pre-existing T cells were expanded. Responses were both CD8+, but also CD4+, indicating that effector T cells received cognate T cell help in the priming process. It is expected that, in particular for patients that are refractory to anti-PD-1 (meaning that activation of pre-existing memory T cells only is not sufficient to mediate clinical activity), combining the vaccine with anti-PD-1 (which would rescue newly primed T cells specificities from exhaustion) is synergistic. This expectation is supported by data from non-clinical experiments.

Arm 1A and Arm 2 of the proposed clinical trial explores a combination of BNT112 and cemiplimab, anti-PD-1 antibody. Antibodies to PD-1/PDL-1 have been shown to be effective therapeutic options for cancer treatment. Cemiplimab is a fully human monoclonal antibody against PD-1 and is currently being evaluated in patients with advanced solid malignancies and B-cell lymphomas whose cancer are incurable and/or have failed to respond to or showed tumor progression despite standard therapy, or patients who are not candidates for standard therapy, or for whom no available therapy is expected to convey clinical benefit. Cemiplimab has demonstrated efficacy (based on ORR and DoR) and is approved in the U.S. for patients with advanced CSCC, NSCLC, and BCC. Patients in Arm 1b will be given the option to be treated with cemiplimab monotherapy after progression with BNT112 monotherapy.

In addition to the potential safety risks, there is a potential unknown risk related to a delayed radical prostatectomy in patients with newly diagnosed LPC. In order to address this risk, patients will be followed for up to 12 months after the last dose of either IMP and the treating physicians will be able to adjust the treatment also during the course of the trial in case earlier intervention is needed.

In summary, the potential benefits of the proposed trials include clinical responses and the generation of lasting T cells against prostate cancer TAAs both in BNT112 monotherapy and in combination with cemiplimab. This could potentially translate into clinically significant and

CONFIDENTIAL Page 42 of 122

durable efficacy, which is of prime importance to patients and outweighs the potential risks outlined above. This warrants development of BNT112 in monotherapy and in combination with cemiplimab in patients with various stages of prostate cancer.

Furthermore, the clinical data generated with the RNA-LPX cancer vaccines thus far in melanoma, TNBC and HPV+ cancers in monotherapy and in combination with anti-PD-1 antibodies demonstrate a positive risk-benefit assessment and warrant further development of the RNA-LPX cancer vaccine in new indications, such as prostate cancer. The safety profile of cemiplimab is similar to the safety profile of other anti-PD-1/PD-L1. The important identified risks are immune-related AEs and injection-related reactions. Based on the currently available safety information for cemiplimab, safety information from other anti-PD-1 antibodies, the adequate risk identification and minimization described in the cemiplimab IB/protocols/ICFs, the emerging preliminary activity of cemiplimab on solid malignancies (including CSCC, NSCLC, and cervical cancer), the benefit-risk is considered favorable for continued clinical trials in these and other indications.

For further information about the known and potential risks of BNT112 and cemiplimab, refer to the latest version of the respective IB (BNT112 or cemiplimab).

# 3. Objectives and Endpoints

Trial objectives and endpoints are listed in Table 3-1.

Table 3-1: Objectives and endpoints of the clinical trial

OBJECTIVES	ENDPOINTS
PRIMARY OBJECTIVE	PRIMARY ENDPOINTS
• (Part 1 and Part 2) Assess safety and tolerability profile of BNT112 monotherapy or in combination with cemiplimab	
 
Occurrence of DLTs.
 
Occurrence of TEAEs reported by relationship, grade, and seriousness according to NCI CTCAE v5.0.
 

(Part 2 Arms 1a and 1b)     Evaluate preliminary antitumor activity of BNT112     monotherapy and in combination with cemiplimab in patients with mCRPC based on ORR	• ORR, defined as the number of patients with a CR or PR per PCWG3  as determined by the investigator as best objective response divided by the number of patients in the analysis set.
SECONDARY OBJECTIVES	SECONDARY ENDPOINTS
• Evaluate anti-tumor activity based on levels of PSA	• PSA decline of 0 to 25%, >25% to 50%, and >50% compared to baseline.
	• PSADT post-treatment on C4D1 and D1 of every fourth subsequent cycle (e.g., C8D1, C12D1, etc.) in Part 1 and Part 2 Arm 1A and 1B, or on C4D1, C8D1, and EoT in Part 2 Arms 2 and 3 compared to baseline.

CONFIDENTIAL Page 43 of 122

OBJECTIVES	ENDPOINTS					
	• PSA decline of ≥50% (according to the PCWG3).					
(Part 1) Evaluate preliminary anti-tumor activity of BNT112 monotherapy in patients with mCRPC based on ORR	• ORR, defined as the number of patients with a CR or PR per PCWG3  as determined by the investigator as best objective response divided by the number of patients in the analysis set.					
Evaluate preliminary anti-tumor activity of BNT112 monotherapy or in combination with cemiplimab in patients with newly diagnosed LPC	Tumor response post-treatment compared to baseline.					
EXPLORATORY OBJECTIVES	EXPLORATORY ENDPOINTS					
Determine systemic induction/expansion of BNT112 antigen-specific T cells for BNT112 monotherapy or in combination with cemiplimab	
 
Occurrence of de novo induction or increase of BNT112 antigen-specific T cells in peripheral blood under treatment on C3D15, and/or C8D15, EoT, or safety follow-up compared to baseline.
 
					
• Evaluate preliminary anti-tumor activity of BNT112 monotherapy and in combination with cemiplimab	
 
DoR, defined as the time from the first occurrence of a documented OR to the time of the first disease progression per PCWG3, as determined by the investigator, or death from any cause, whichever occurs first.
 
					
in patients with mCRPC	
 
ORR and DoR, defined as above, using iRECIST.
 
					
	• PFS, defined as the time from the first trial treatment to the first disease progression per PCWG3,  as determined by the investigator, and per iRECIST  determined by central reading, or death from any cause, whichever occurs first.					
	• OS, defined as the time from first trial treatment until death from any cause.					
	
 
Number of cycles received and RDI.
 
					
• Evaluate preliminary anti-tumor activity of cemiplimab in patients with mCRPC who have been previously treated with,	
 
ORR, defined as the number of patients with a CR or PR per PCWG3 as determined by the investigator as best objective response divided by the number of patients in the analysis set.
 
					
and who have progressed after BNT112 monotherapy	
 
DoR, defined as the time from the first occurrence of a documented OR to the time of the first disease progression per PCWG3, as determined by the investigator, or death from any cause, whichever occurs first.
 
					
	• ORR and DoR, defined as above, using iRECIST.					
	
 
PFS, defined as the time from the first trial treatment to the first disease progression per PCWG3, as determined
 
					

CONFIDENTIAL Page 44 of 122

OBJECTIVES	ENDPOINTS
	by the investigator, and as per iRECIST determined by central reading, or death from any cause, whichever occurs first.
	• PFS2, defined as the time from the first trial treatment to the first disease progression after start of cemiplimab per PCWG3 as determined by the investigator, or death from any cause, whichever occurs first.
	• OS, defined as the time from first trial treatment until death from any cause.
	
 
Number of cycles received and RDI.
 

Assess safety and tolerability profile of cemiplimab monotherapy in patients following progression after BNT112 monotherapy	Occurrence of TEAEs reported by relationship, grade, and seriousness according to NCI CTCAE v5.0.

 
Evaluate preliminary anti-tumor activity of BNT112 monotherapy or in combination with cemiplimab in patients
 
	
 
PFS, defined as the time from the first trial treatment to the first disease progression per PCWG3 as determined by the investigator, or death from any cause, whichever occurs first.
 

with newly diagnosed LPC	• OS, defined as the time from first trial treatment until death from any cause.

 
Preliminary assessment of biomarkers that might act as potential predictive,
 
	• Status of tumor mutational burden and immune-related gene expression (at the RNA level) in tumor tissue prior to treatment.
pharmacodynamics, anti-tumor, and safety indicators of activity of BNT112 monotherapy or in combination with cemiplimab	
 
Change in protein expression pattern/levels of tumor microenvironment markers (e.g., CD3, CD8, MHC-I, PD-L1, etc.) and prostate tumor markers (e.g., PSA, PSAP, NKX3-1, etc.) in tumor tissue post-treatment compared to baseline.
 

	
 
Baseline status or change in RNA target expression of BNT112-encoded antigens in the post-treatment tissue compared to baseline.
 

	• Change in T cell clonality/diversity post-treatment compared to baseline.
	
 
Changes in blood biomarkers prior to and during trial treatment.
 

ENIDDOMES

Abbreviations: AE = adverse event; C = Cycle; CR = complete response; CTCAE v5.0 = Common Terminology Criteria for Adverse Events, version 5.0; D = Day of cycle; DLT = dose-limiting toxicity; DoR = duration of response; EoT = End of Treatment; iRECIST = immune-modified Response Evaluation Criteria in Solid Tumors; MHC = major histocompatibility complex; NCI = National Cancer Institute; NKX3-1 = NK3 homeobox 1; OR = objective response; ORR = objective response rate; PCWG3 = Prostate Cancer Working Group 3; PD-L1 = programmed cell death 1 ligand 1; PFS = progression-free survival; PR = partial response; PSA = prostate-specific antigen; PSADT = prostate-specific antigen doubling time; PSAP = prostate-specific acid phosphatase; RDI = relative dose intensity.

CONFIDENTIAL Page 45 of 122

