#### **ENDPOINTS**

- ORR, defined as the number of patients with a CR or PR per PCWG3 as determined by the investigator as best objective response (OR) divided by the number of patients in the analysis set.
- DoR, defined as the time from the first occurrence of a documented OR to the time of the first disease progression per PCWG3, as determined by the investigator, or death from any cause, whichever occurs
- ORR and DoR, defined as above, using iRECIST.
- PFS, defined as the time from the first cemiplimab treatment to the first disease progression per PCWG3 as determined by the investigator, and per iRECIST determined by central reading, or death from any cause, whichever occurs first.
- PFS2, defined as the time from the first trial treatment to the first disease progression after start of cemiplimab per PCWG3 as determined by the investigator, or death from any cause, whichever occurs first.
- OS, defined as the time from first trial treatment until death from any cause.
- Number of cycles received and RDI.
- Assess safety and tolerability profile of cemiplimab monotherapy in patients following progression after BNT112 monotherapy
- Occurrence of TEAEs reported by relationship, grade, and seriousness according to NCI CTCAE v5.0.
- Evaluate preliminary anti-tumor activity of BNT112 monotherapy or in combination with cemiplimab in patients with newly diagnosed LPC
- PFS, defined as the time from the first trial treatment to the first disease progression per PCWG3 as determined by the investigator, or death from any cause, whichever occurs first.
- OS, defined as the time from first trial treatment until death from any cause.
- Preliminary assessment of biomarkers that might act as potential predictive, pharmacodynamics, anti-tumor, and safety indicators of activity of BNT112 monotherapy or in combination with cemiplimab
- Status of tumor mutational burden and immune-related gene expression (at the ribonucleic acid [RNA] level) in tumor tissue prior to treatment.
- Change in protein expression pattern/levels of tumor microenvironment markers (e.g., CD3, CD8, MHC-I, PD-L1, etc.) and prostate tumor markers (e.g., PSA, PSAP, NKX3-1, etc.) in tumor tissue post-treatment compared to baseline.

CONFIDENTIAL Page 12 of 122

OBJECTIVES	EN	NDPOINTS
	•	Baseline status or change in RNA target expression of BNT112—encoded antigens in the post-treatment tissue compared to baseline.
	•	Change in T cell clonality/diversity post-treatment compared to baseline.

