#### Abbreviations and Footnotes:

X& = to be done before IMP administration; XS = to be done after IMP administration; X&S = to be done before and after IMP administration; (X) = optional; AE = adverse event; C = cycle (One cycle is defined as 21 days); D = day of cycle; d = day(s); DLT = dose-limiting toxicity; ECG = electrocardiogram; ECOG PS = Eastern Cooperative Oncology Group performance status; h = hour(s); ELISpot = enzyme linked immunospot (assay); EoT = End of Treatment; FFPE = formalin-fixed, paraffin-embedded; FU = follow-up; HLA = human leukocyte antigen; IMP = investigational medicinal product; PSA = prostate-specific antigen; SRC = Safety Review Committee; TCR = T cell receptor; TEAE = treatment-emergent AE; UV = unscheduled visit.

CONFIDENTIAL Page 28 of 122

Starting with C3D1, treatment will be administered every 3 weeks until a discontinuation-of-treatment criterion is met. Planned visit schedule until C8 is shown in table. From Cycle 8 on, coagulation, blood chemistry, hematology, and urinalysis will be measured every second cycle (i.e., C8, C10, C12, etc.) unless clinically indicated.

- \* EoT assessments will be performed up to 21 days after administration of the last dose of IMP for patients who discontinued trial treatment, except if patient was lost to follow-up or died or the EoT visit may be combined with the Safety FU-D30 visit. For patients of Arm 1B who will optionally start cemiplimab monotherapy as outlined in the Schedule of Activities shown in Section 1.5, the EoT visit may be combined with visit CemC1 if both visits are to happen with less than 7 days difference.
- \*\* All patients (Part 1 and 2) will be actively followed up for safety (FU-D30) after last intake of BNT112. Patients in Part 2 Arm 1A will be followed up for safety (FU-D90) after last intake of cemiplimab or (FU-D30) after last intake of BNT112, whichever is later. All patients will be followed up for efficacy (FU-M6 after the last intake of IMP, FU-M12 after the last intake of IMP). Within 28 days after confirmation of disease progression, patients of Arm 1B can optionally start cemiplimab monotherapy and will follow the Schedule of Activities shown in Section 1.5 after performing the EoT for BNT112 treatment.

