# **8.1.1.2.** Tumor Response Assessment

### Part 1 and Part 2 Arms 1A and 1B

In patients with mCRPC, response to treatment with BNT112 as monotherapy or in combination with cemiplimab will be assessed for the following outcome measures based on post-baseline radiographic images as defined above.

- ORR (CR or PR) using PCWG3 criteria and iRECIST criteria
- DoR, using PCWG3 criteria
- PFS using PCWG3 criteria and iRECIST criteria
- Criteria for disease response assessment are provided in Appendix 9.

The PCWG3 criteria will be used for endpoint response evaluation as well as follow-up tumor assessment and will be done by a local radiologist.

The iRECIST criteria will be used for exploratory endpoint response evaluation and will be done retrospectively centrally by an imaging laboratory.

Patients in Arm 1B will be given the option to be treated with cemiplimab monotherapy following progression on BNT112 monotherapy treatment and will be assessed for the same outcome measures as listed above, where the last measurement prior to start of cemiplimab treatment will serve as baseline measurement and the time-to-event endpoints (DoR, and PFS) will start from first dose of cemiplimab treatment. In particular, the last radiographic tumor assessment prior to cemiplimab treatment will re-define target and non-target lesions as basis for tumor response assessment on cemiplimab treatment. Additionally, PFS2 will be evaluated based on initial treatment.

### Part 2 Arms 2 and 3

In patients with LPC, response to neoadjuvant treatment with BNT112 plus cemiplimab (Part 2 Arm 2) and BNT112 alone (Part 2 Arm 3) will be assessed for the following outcome measure based on post-baseline radiographic images as defined above:

• mpMRI or MRI tumor assessment post-treatment compared to baseline.

The tumor assessment will be used for endpoint response evaluation and will be done by a local radiologist; in addition, based on the sponsor's decision, a central read by an imaging laboratory can be added. The same imaging modality should be used at screening and at all subsequent assessments.

CONFIDENTIAL Page 74 of 122

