Pharmacodynamic	The pharmacodynamic set is defined as all patients who have received IMP (i.e., at least 1 dose of W_pro1 and/or cemiplimab) and with a baseline and at least 1 on-treatment/post-treatment follow-up

Population	Description
	pharmacodynamic assessment as specified in Section 8.8.1 (i.e. Hormones (Testosterone), Cytokines).
Subsequent Cemiplimab Monotherapy on Progression (Cemi Mono on PD)	Only applicable for Part 2 Arm 1B: The subsequent cemiplimab monotherapy on progression set (Cemi Mono on PD) is defined as all mCRPC patients in Arm 1B (W_pro1 monotherapy) who switch to cemiplimab monotherapy after disease progression and who received at least one dose of cemiplimab.

The DLT evaluation set will be used for the evaluation of DLTs in order to assess the REDR in Part 1 of the trial.

The safety set will be used for all other safety analyses, while the mITT set will be used as primary analysis set for efficacy analyses.

The subsequent cemiplimab monotherapy on progression set will be used for all exploratory safety and efficacy analyses for the Arm 1B patients who received cemiplimab (i.e., at least 1 dose of cemiplimab) after progression to W_pro1 monotherapy.

The ITT analysis set will be used for disposition analyses.

Further, the ITT and PP sets will be used for sensitivity analyses of some predefined efficacy endpoints depending on the number of patients excluded. If none of the patients are excluded from the mITT set, compared to the ITT set, or if the number of patients excluded from the PP set is small (exclusion rate $\leq 10\%$), no additional sensitivity analyses for the ITT or the PP set will be generated. The final decision to perform sensitivity analyses for the ITT set or for the PP set will be made during the DRM meeting for the final analysis.

All safety analyses and analyses based on the Pharmacodynamic set will be based on the treatment actually taken by the patient (“as treated”).

All other analyses will be based on the treatment the patient was assigned/randomized to (“as randomized”), unless stated otherwise.

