(MIN [Date of first documented disease progression (iCPD) after start of cemiplimab treatment, date of death from any cause] – Date of first documented overall response (iCR or iPR) + 1) / 30.4375 for events

or

(Date of the last evaluable response assessment after start of cemiplimab treatment – Date of first documented overall response (iCR or iPR) + 1) / 30.4375 in case of censoring.

Progression-free survival based on PCWG3 or iRECIST (central reading)

PFS will be analyzed separately for PCWG3 and iRECIST (central reading).

PFS is defined as the time from the date of the first dose of cemiplimab treatment to the date of the first disease progression, or death from any cause, whichever occurs first.

Only death dates reported prior to or at the date of trial discontinuation will be considered in the PFS analysis.

PFS will be analyzed using the Kaplan-Meier method. Kaplan-Meier plots will be generated.

Patients alive and without disease progression after start of cemiplimab treatment at the data cut-off date or patients lost to follow-up will be censored at the day of their last response assessment.

Only response assessments prior to or at the start date of the first subsequent anti-cancer therapy will be considered for PFS analysis. PD within 14 days after the start date of the first subsequent anti-cancer therapy will be considered.

If no post-baseline response assessment after start of cemiplimab treatment is available, the patient will be censored at the date of the first dose of cemiplimab treatment.

PFS expressed in months = (MIN [Date of first disease progression after start of cemiplimab treatment, Date of death from any cause] – date of first dose of cemiplimab treatment + 1) / 30.4375 if the patient has a PFS event

or

(Date of last evaluable response assessment after start of cemiplimab treatment – date of first dose of cemiplimab treatment + 1) / 30.375 in case of censoring.

Progression-free survival 2 (PFS2) based on PCWG3

PFS2 is defined as the time from the date of the first IMP to the date of the first disease progression after start of cemiplimab per PCWG3, or death from any cause, whichever occurs first.

Only death dates reported prior to or at the date of trial discontinuation will be considered in the PFS2 analysis.

PFS2 will be analyzed using the Kaplan-Meier method. Kaplan-Meier plots will be generated.

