Patients alive and without disease progression after start of the first IMP at the data cut-off date or patients lost to follow-up will be censored at the day of their last response assessment. Only response assessments prior to or at the start date of the first subsequent anti-cancer therapy will be considered for PFS2 analysis. PD within 14 days after the start date of the first subsequent anti-cancer therapy will be considered.

If no post-baseline response assessment after start of cemiplimab treatment is available, the patient will be censored at the date of the first dose of cemiplimab treatment.

PFS2 expressed in months = (MIN [Date of first disease progression after start of cemiplimab treatment, Date of death from any cause] – date of first dose IMP + 1) / 30.4375 if the patient has a PFS2 event

or

(Date of last evaluable response assessment after start of cemiplimab treatment – date of first dose of IMP + 1) / 30.375 in case of censoring.

Overall survival for the subset of patients in Arm 1B who are treated with cemiplimab monotherapy

OS is defined as the time from the date of first dose of IMP to the date of death from any cause. OS will be analyzed using the Kaplan-Meier method. Kaplan-Meier plots will be generated. OS expressed in months will be derived as defined in Section 8.7.4.1.

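### Protocol Table 3-1 starts PFS on cemiplimab for Arm 1B switchers at the first trial treatment, against the synopsis, protocol 8.1.1.2 and the SAP; SAP 8.7.4.2 has two related slips

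*Protocol*

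**What the plan says.** Protocol Table 3-1, under the objective on cemiplimab in mCRPC patients who progressed after BNT112 monotherapy, has "PFS, defined as the time from the first trial treatment to the first disease progression per PCWG3, as determined" by the investigator. The line continues with iRECIST by central reading and with death. The next endpoint in the table is PFS2, which also starts at first trial treatment but counts only progression after the start of cemiplimab.

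The synopsis, for the same objective, has "PFS, defined as the time from the first cemiplimab treatment to the first disease progression per PCWG3 as determined by the investigator". SAP Table 3-1 uses the same origin. Protocol 8.1.1.2 says that for switchers "the time-to-event endpoints (DoR, and PFS) will start from first dose of cemiplimab treatment". SAP 8.7.4.2 states "PFS is defined as the time from the date of the first dose of cemiplimab treatment to the date of the first disease progression", and its formula takes the first progression after the start of cemiplimab.

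On the order of events, a footnote to the schedule in protocol 1.3 says "Within 28 days after confirmation of disease progression, patients of Arm 1B can optionally start cemiplimab monotherapy". The analysis set in SAP 7.1 consists of Arm 1B patients "who switch to cemiplimab monotherapy after disease progression and who received at least one dose of cemiplimab".

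For PFS2, the censoring sentence in SAP 8.7.4.2 begins "Patients alive and without disease progression after start of the first IMP at the data cut-off date or patients lost to follow-up". The event and censoring formulas below it refer to progression and assessments after the start of cemiplimab.

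**The concern.** An endpoint meant to describe cemiplimab has to run over time on cemiplimab. In Table 3-1 both its start and, read literally, its end lie before the first cemiplimab dose. Table 3-1 is the protocol's formal endpoint list, so a report or registry entry drawn from it would misdescribe this PFS. The SAP departs from the table without recording it: Appendix 1, which lists changes to protocol-planned analyses, covers the added analysis sets but not this definition.

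The two SAP slips sit in the text a programmer would follow. The PFS2 sentence describes the wrong patients for censoring, and the censored PFS and PFS2 times use a different month length from the event times.

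**Working it through.** The plan states no figure for this endpoint, so there is nothing to reproduce. The check is a comparison of definitions.

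**Order of events.** For a switcher, let T0 be the first BNT112 dose, P1 the progression on BNT112, C the first cemiplimab dose, and P2 the first progression or death after C. Protocol 1.3 and SAP 7.1 require progression before the switch, so T0 < P1 < C < P2.

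**What each definition measures.** The SAP adds one day to every duration; this does not affect the comparison.

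| Definition | Interval |
|---|---|
| Protocol Table 3-1, literal | P1 − T0, the PFS on BNT112 |
| Protocol Table 3-1, read as progression after cemiplimab start | P2 − T0 |
| PFS2, protocol Table 3-1 and SAP | P2 − T0 |
| SAP 8.7.4.2 formula; origin as in the synopsis and protocol 8.1.1.2 | P2 − C |

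The literal reading contains neither C nor P2. The other reading of Table 3-1 is identical to PFS2, and exceeds the intended PFS by C − T0, the whole time before cemiplimab.

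**Illustration.** A simulation of 200,000 switchers shows the consequence. All its inputs are assumptions: time to progression on BNT112 exponential with median 3 months, gap to cemiplimab uniform on 0 to 28 days, and PFS on cemiplimab exponential with the median varied. Simulated medians in months:

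| Assumed cemiplimab median | Table 3-1 literal | From first cemiplimab | PFS2 |
|---|---|---|---|
| 1 | 2.98 | 1.00 | 5.03 |
| 2 | 2.98 | 2.00 | 6.46 |
| 4 | 2.98 | 3.99 | 8.89 |
| 8 | 2.98 | 7.98 | 13.13 |
| 16 | 2.98 | 15.96 | 21.09 |

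The literal Table 3-1 value does not move, and its correlation with time on cemiplimab is 0.0. That follows from the definition; the particular medians only reflect the assumed inputs.

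**PFS2 censoring sentence.** Its first limb requires no progression since the first IMP. P1 lies after T0 for every switcher, so nobody meets it. The formula below requires only that there be no progression after C. Sentence and formula disagree.

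**Month length.** SAP 8.2 sets one month at 30.4375 days. In SAP 8.7.4.2 the event formulas for PFS and PFS2 use 30.4375, while the censored formulas use 30.375. The ratio is 30.4375 / 30.375 = 1.002, so censored times come out 0.2% too long. For a true 6 months: 6 × 30.4375 = 182.625 days, and 182.625 / 30.375 = 6.01 months.

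**The case against.** The strongest reply is that the analysis is already settled. Table 3-1 is the lone outlier, probably carried over from the mCRPC row above it, where the wording is correct. Protocol 9.4 leaves the detailed analysis to the SAP, and the SAP gives a full formula from first cemiplimab. The endpoint is exploratory, tests no hypothesis, and concerns an optional subset of an arm whose enrollment stopped after the interim analysis. All of this stands, and it keeps the point minor. It does not make Table 3-1 correct, and it does not touch the two slips inside the SAP.

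Three stronger readings are tempting, and the documents do not support them.

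- A reader might infer that the Table 3-1 endpoint carries no information on cemiplimab at all. That is strict only for investigator-assessed PCWG3 progression. The same line covers iRECIST by central reading, done retrospectively; a central read could date first progression after the switch, so that component is mixed rather than empty.
- A reader might put a minimum on the added time from the first scheduled scan at C3D15 and the 28-day switch window. The scan is no minimum: protocol 8.1.1.1 allows additional scans at the investigator's discretion, and Appendix 9 accepts clinical progression. The window is not fixed either: the footnote in protocol 1.3 counts it from confirmation of progression, the table in 1.5 from progression.
- A reader might infer that the PFS2 sentence leaves some switchers without a PFS2 time. The formulas, with the rule for patients lacking an assessment after cemiplimab start, still give every switcher one. The PFS2 origin is right throughout.

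**Conclusion.** The definition in protocol Table 3-1 is wrong as written; severity is minor. For investigator-assessed PCWG3 progression it yields either the BNT112 PFS or a copy of PFS2, and neither measures PFS on cemiplimab. This rests only on the requirement that switchers have progressed before their first cemiplimab dose. No analysis result changes if SAP 8.7.4.2 is followed for PFS. No defensible figure for the added time can be drawn from the documents.

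The PFS2 censoring sentence contradicts its formula but leaves no patient without a time. The wrong month length lengthens censored PFS and PFS2 by 0.2%. No primary or secondary endpoint is involved.

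**What to change.** 1. **Protocol Table 3-1.** For this objective, run PFS from the first cemiplimab treatment to the first progression dated after cemiplimab start (PCWG3 by investigator; iRECIST by central reading) or death, whichever is earlier. The event must be qualified as well as the origin: with only the origin changed, a literal first progression would still precede cemiplimab and give negative times.
2. **SAP 8.7.4.2, PFS2.** In the censoring sentence, replace the reference to the first IMP with the start of cemiplimab treatment, to match the formula.
3. **SAP 8.7.4.2, censored PFS and PFS2 formulas.** Replace 30.375 with 30.4375.
4. **SAP Appendix 1.** If the protocol table is not amended, list the different PFS definition there.

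The cost is a few words and one constant. Data collection, treatment and sample size do not change.
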